8.6 Follow-up of subjects withdrawn from treatment

Subjects that are withdrawn will not be followed.

8.7 Premature termination of the study

The study will be halted when there are any problems with the closed loop controller reported by the clinical staff. Problems are defined as frequent fluctuations around the target range, in ability to correct the saturation to within the intended target range (excluding the cases when it runs into the minimum or maximum allowed FiO_2 as set by the clinical staff). When it is determined that the problem is caused by the algorithm or the implementation of the algorithm with in the Fabian HFO ventilator, the study will be terminated prematurely.

9. SAFETY REPORTING

9.1 Temporary halt for reasons of subject safety

In accordance to section 10, subsection 4, of the WMO, the sponsor will suspend the study if there is sufficient ground that continuation of the study will jeopardise subject health or safety. The sponsor will notify the accredited METC without undue delay of a temporary halt including the reason for such an action. The study will be suspended pending a further positive decision by the accredited METC. The investigator will take care that all subjects are kept informed.

9.2 AEs, SAEs and SUSARs

9.2.1 Adverse events (AEs)

Adverse events are defined as any undesirable experience occurring to a subject during the study, whether or not considered related to [the investigational product / trial procedure/ the experimental intervention]. All adverse events reported spontaneously by the subject or observed by the investigator or his staff will be recorded.

9.2.2 Serious adverse events (SAEs)

A serious adverse event is any untoward medical occurrence or effect that

- results in death;
- is life threatening (at the time of the event);
- requires hospitalisation or prolongation of existing inpatients' hospitalisation;
- results in persistent or significant disability or incapacity;
- is a congenital anomaly or birth defect; or
- any other important medical event that did not result in any of the outcomes listed above due to medical or surgical intervention but could have been based upon appropriate judgement by the investigator.

An elective hospital admission will not be considered as a serious adverse event.

The investigator will report all SAEs to the sponsor without undue delay after obtaining knowledge of the events, except for the following SAEs:

The sponsor will report the SAEs through the web portal *ToetsingOnline* to the accredited METC that approved the protocol, within 7 days of first knowledge for

SAEs that result in death or are life threatening followed by a period of maximum of 8 days to complete the initial preliminary report. All other SAEs will be reported within a period of maximum 15 days after the sponsor has first knowledge of the serious adverse events.

9.2.3 Suspected unexpected serious adverse reactions (SUSARs)

Adverse reactions are all untoward and unintended responses to an investigational product related to any dose administered.

Unexpected adverse reactions are SUSARs if the following three conditions are met:

- 1. the event must be serious (see chapter 9.2.2);
- there must be a certain degree of probability that the event is a harmful and an undesirable reaction to the medicinal product under investigation, regardless of the administered dose;
- 3. the adverse reaction must be unexpected, that is to say, the nature and severity of the adverse reaction are not in agreement with the product information as recorded in:
 - Summary of Product Characteristics (SPC) for an authorised medicinal product;
 - Investigator's Brochure for an unauthorised medicinal product.

The sponsor will report expedited the following SUSARs through the web portal *ToetsingOnline* to the METC

- □ SUSARs that have arisen in the clinical trial that was assessed by the METC;
- SUSARs that have arisen in other clinical trials of the same sponsor and with the same medicinal product, and that could have consequences for the safety of the subjects involved in the clinical trial that was assessed by the METC. The remaining SUSARs are recorded in an overview list (line-listing) that will be submitted once every half year to the METC. This line-listing provides an overview of all SUSARs from the study medicine, accompanied by a brief report highlighting the main points of concern.

The expedited reporting of SUSARs through the web portal Eudravigilance or ToetsingOnline is sufficient as notification to the competent authority. The sponsor will report expedited all SUSARs to the competent authorities in other Member States, according to the requirements of the Member States.

The expedited reporting will occur not later than 15 days after the sponsor has first knowledge of the adverse reactions. For fatal or life threatening cases the term will be maximal 7 days for a preliminary report with another 8 days for completion of the report.

9.3 Annual safety report

In addition to the expedited reporting of SUSARs, the sponsor will submit, once a year throughout the clinical trial, a safety report to the accredited METC, competent authority, and competent authorities of the concerned Member States. This safety report consists of:

- a list of all suspected (unexpected or expected) serious adverse reactions, along with an aggregated summary table of all reported serious adverse reactions, ordered by organ system, per study;
- a report concerning the safety of the subjects, consisting of a complete safety analysis and an evaluation of the balance between the efficacy and the harmfulness of the medicine under investigation.

9.4 Follow-up of adverse events

All AEs will be followed until they have abated, or until a stable situation has been reached. Depending on the event, follow up may require additional tests or medical procedures as indicated, and/or referral to the general physician or a medical specialist. SAEs need to be reported till end of study within the Netherlands, as defined in the protocol

9.5 [Data Safety Monitoring Board (DSMB) / Safety Committee]

A DSMB or Safety Committee is not needed.

10.STATISTICAL ANALYSIS

All analysis will be done on a intention to treat, with reporting on the time that the automated algorithm was disabled and the number of manual adjustments to ensure that the algorithm was doing the fast majority of the adjustments. Every time the algorithm disables the reason is recorded and will be reported. All manual adjustments that are

performed during the automated control period will be assessed and the possible reason reported.

Because analysis are performed on a per time basis, missing data does not affect the outcome. The amount of missing data, if any, will be reported.

10.1 Primary study parameter(s)

The efficiency of the PRICO algorithm will be assessed by comparing the time spend outside and deviation from the SpO₂ target range. This is done with the area under the curve, normalized to a one hour period [SpO₂*min per hour]. It is calculated by taking the SpO₂ value from the patient monitor, logged once every second and, when it is outside the SpO₂ target range, subtract the target. The absolute value of all deviations is added together and divided by the length of all the recorded data in hours. The significance will be tested with a repeated measurement ANOVA.

The number of collected data points per period will be reported to show any possible bias due to unmeasurable SpO₂ levels, malfunctions or other events. This will be reported as a percentage of time recorded.

When there is a significant difference between the first and last period, the argument will be made that the patient changed overtime. In that case the automated period will be compared with the best of the two observational periods.

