4.2 Inclusion criteria

In order to be eligible to participate in this study, a subject must meet all of the following criteria:

Neonates admitted to the NICU in the Erasmus MC, Rotterdam and Máxima Medical Centre, Veldhoven that are receiving respiratory support and a FiO_2 of more than 21% while having SpO₂ of 95% or less. No plans to change ventilation mode within the next 24 hours.

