8. METHODS

8.1 Study parameters/endpoints

8.1.1 Main study parameter/endpoint

The main study parameter is the oxygen saturation measured with a pulse oximeter (SpO_2) . The goal is to stay within the SpO_2 target range. The range is dependent on the gestational age (GA) of the neonate:

 Table 1: Oxygen saturation targets form the Erasmus MC - Sophia (2015)

-	Prematuren <37 weken met zuurstoftoediening	89-95%
-	Prematuren <37 weken met NO-toediening	92-98%
-	A term neonaten met zuurstoftoediening	92-96%
-	A term neonaten met NO-toediening	92-98%

The main parameter is the area outside of the SpO_2 target range. This gives an indication of both the time outside of the target range as well as the deviation from the target. The number of times the SpO_2 is above and or below the target range is logged, as is the duration of the event and the average deviation from the target.

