8.4 Withdrawal of individual subjects

Subjects can leave the study at any time for any reason if they wish to do so without any consequences. The investigator can decide to withdraw a subject from the study for urgent medical reasons.

When patients improve and no longer need additional oxygen, they will drop out of the study, if it occurs before the completion of the automated FiO₂ phase.

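### The primary AUC counts SpO2 above the upper limit at FiO2 21% as control failure, and the withdrawal rule lets sustained room-air time build up only in the last manual block

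*Protocol*

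**What the plan says.** Section 10.1 of the Protocol defines the primary measure completely. Each one-second SpO2 value outside the target has the target subtracted, and then "The absolute value of all deviations is added together and divided by the length of all the recorded data in hours". Section 8.1.1 describes the same area and says of it: "This gives an indication of both the time outside of the target range as well as the deviation from the target". Neither section makes the calculation depend on FiO2.

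Table 1 in section 8.1.1 ties the two non-NO ranges to oxygen administration: 89-95% for "Prematuren <37 weken met zuurstoftoediening" and 92-96% for "A term neonaten met zuurstoftoediening". The NO rows, such as "Prematuren <37 weken met NO-toediening" (92-98%), are not tied to added oxygen. No range is given for an infant in room air without NO. At entry every infant has an FiO2 "of more than 21% while having" an SpO2 of 95% or less (section 4.2).

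Section 8.4 says of infants who improve and need no more oxygen that "they will drop out of the study, if it occurs before the completion of the automated" FiO2 phase. Section 8.5 equates this state with FiO2 of 21%, and section 8.6 says withdrawn infants are not followed. The order is fixed: 8 hours manual, 8 hours automated, 8 hours manual (section 8.2).

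Section 8.7, on halting the study, does not count failure to correct saturation as a controller problem at the FiO2 bounds: "excluding the cases when it runs into the minimum or maximum allowed" FiO2 as set by staff.

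**The concern.** The endpoint is meant to measure how well oxygen is controlled. At FiO2 21% neither nurse nor algorithm can lower anything, and outside NO treatment Table 1 gives no range for that state. A recovering infant at 97-100% in room air nevertheless accumulates AUC as if badly controlled.

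This would be mostly noise if it fell evenly on the three blocks, but it does not. An infant weaned for good during the first manual or the automated block leaves the study and builds up little room-air time. An infant weaned during the last manual block stays, and every later above-limit second enters that block. The order of blocks is neither randomised nor counterbalanced, so the manual condition alone carries this load. Recovery can then be read as a benefit of PRICO.

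**Working it through.** **Planned effect.** Section 4.4 gives a fall in mean AUC from 21 to 3 (difference 18), SD 30, 5% significance and 80% power. With two-sided alpha and a paired normal formula, n = ((1.960 + 0.842) × 30 / 18)² = 21.8, rounded up to 22. This is the stated number per stratum, so 18 and 30 are the right yardsticks. Units below are %SpO2·min per hour.

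**One infant.** Addition to its own block = (SpO2 − upper limit) × 60 × share of the block in room air. The upper limit is 95% (preterm, no NO). Room-air SpO2 is an assumption, since the Protocol gives no figure.

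- 99% for 1 of 8 hours: 4 × 60 × 1/8 = 30
- 97% for 1 of 8 hours: 2 × 60 × 1/8 = 15
- 98% for half the block: 3 × 60 × 1/2 = 90

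**Mean of a 22-infant stratum.** The planned effect is a group mean, so these values must be divided by 22.

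- One infant at 99% for 1 hour: 30/22 = 1.4 (8% of 18)
- One infant at 98% for half the block: 90/22 = 4.1 (23% of 18)
- Two infants at 98% for half the block: 180/22 = 8.2 (45% of 18)

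If the two manual blocks are averaged, each shift is halved.

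**Effect on the test.** I simulated no true effect with n = 22 and an SD of 30 for the difference between two blocks. A proportion of infants was weaned in the last block, each with a uniform 0-100% share of that block in room air. The last-block comparison is a paired t-test. The second comparison averages the manual blocks, but switches to the manual block with the lower mean when the first and last differ at 5%, as section 10.1 directs. Paired t-tests stand in for the planned repeated-measures ANOVA. Entries are the chance of a significant result favouring PRICO; the nominal value is 2.5%.

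| Weaned in last block | Room-air SpO2 | Last manual vs automated | Manual averaged, better-block rule applied |
|---|---|---|---|
| 5% | 97% | 4.9% | about 4% |
| 5% | 98% | 4.9% | about 4% |
| 10% | 97% | 8.6% | about 6% |
| 10% | 98% | 9.9% | about 6% |
| 20% | 97% | 21.9% | about 9% |
| 20% | 98% | 28.6% | about 11% |

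At 98% in room air, the test between the two manual blocks reaches significance, and so triggers the better-block rule, in only about 6%, 10% and 29% of runs at 5%, 10% and 20% weaned. Its rate with nobody weaned is 5%.

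**The case against.** **Existing safeguard.** If the first and last blocks differ significantly, section 10.1 compares PRICO with the better manual block, so a grossly inflated last block would be set aside. This stands in part: the right-hand column of the table is lower because of it. With few infants weaned the rule seldom triggers, and the excess remains.

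**Weaning may be rare.** The 10% dropout in section 4.4 covers withdrawal and improvement together. Spread evenly over the 16 hours in which the withdrawal rule applies (an assumption), that is at most about 5% per 8 hours, where the inflation is small. This is fair, and it makes the 20% rows an upper range rather than an expectation.

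**Net direction.** Short spells at 21% during the automated block count against PRICO and could offset some of the bias. Section 10 calls for intention to treat and does not say that data from infants who leave are discarded. Both points are correct. Even if partial data are kept, though, recording ends when the infant leaves, so sustained room-air time can still build up only in the last block.

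**Supporting passages.** Section 8.7 concerns halting the study, its minimum is set by staff and need not be 21%, and it excuses the maximum as well. It shows that the sponsor recognises a floor effect. It does not show that an exclusion from the endpoint was intended. Table 1 could also be read as classifying infants at entry rather than second by second. That reading leaves unchanged the fact that nothing can be lowered at 21%.

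**Real overshoot.** If FiO2 is cut to 21% while SpO2 is still high, those seconds are true overshoot, which section 13.2 names as the main residual risk. This stands, and it shapes the fix.

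**Conclusion.** The point holds as a moderate bias in how the endpoint is defined. Section 10.1 scores above-limit SpO2 at FiO2 21% as control failure, and section 8.4 lets sustained weaning inflate only the last manual block, in PRICO's favour. That direction for sustained weaning follows from the text. The size does not, because the Protocol gives neither the weaning rate nor room-air SpO2. With 5-20% weaned and 97-98% in room air, the false-positive rate in that direction rises from 2.5% to about 4-11% with manual blocks averaged and the better-block rule applied, and to about 5-29% for last manual against automated alone.

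A reader might infer three stronger things that the document does not support:

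- That one recovering infant outweighs the planned effect. The 30 is that infant's own block value; on a 22-infant mean it is 1.4.
- That the whole comparison is known to favour PRICO. Short spells at 21% in the automated block work the other way, and their frequency is unknown.
- That no target applies at 21% for any infant. The NO ranges are not tied to added oxygen.

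**What to change.** In section 10.1, for infants not on NO, exclude seconds with SpO2 above the upper limit while logged FiO2 is 21% from both the summed deviations and the recorded time, in all three blocks. Keep seconds below the lower limit. Setting the deviation to zero while leaving the time in the denominator would not do: it would credit a recovered infant with perfect control and could make the last manual block look the better one.

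Report time at FiO2 21% per block, and keep the unrestricted AUC as a sensitivity analysis so that overshoot remains visible.

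The cost is one or two sentences in section 10.1 and a short filter in the analysis code. FiO2 is already logged at 1 Hz (Table 2), so no new data are needed, and care and the planned 22 per stratum are unchanged. The downside is that some true overshoot seconds leave the primary measure and the denominator varies slightly between blocks.

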4.4 Sample size calculation

The sample size calculation is based on the area under the curve for the SpO_2 . Giving a value that has a unit of [% SpO_2 *min]. A value of 30 can be reached by a SpO_2 of 30% outside of the target during 1 minute, or 30 minutes a SpO_2 that is 1% outside of the target. Values are normalized per hour.

During the animal trial conducted with this algorithm a reduction in the average of the area under the curve was found from 21 to 3 [%SpO₂*min per hour], with a standard deviation of 30 [%SpO₂*min per hour]. We accepted a significance level of 5% and a power of 80%. Because of the study design, each patient is its own control. Because of that only 22 patients are needed (Stata, StataCorp LP, USA). Because we want to show that the algorithm works in all 3 strata of ventilation we need three groups of 22 patients, and we expect a 10% dropout rate due to withdrawal or improvement in ventilation up to the point that additional oxygen is no longer needed, resulting in a total sample size of 72 patients.

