8.2 Randomisation, blinding and treatment allocation

This study is not randomised nor blinded. It is impossible to safely blind the care giver for the given intervention. The patients are used as their own control to limit the variation and thus the number of patients that have to be included.

Each neonate included in the study will be monitored for 8 hours while receiving routine care. The patient then receives 8 hours of automated control of the FiO_2 . After the intervention there will be another 8 hour observational period during routine care is given. With this setup we can correct for patients that are worsening or improving during the time of the observations.

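### The best-of-two-manual-blocks rule in Protocol 10.1 does not correct for drift over the 24 hours; under linear drift it biases the comparison against PRICO by the drift per block

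*Protocol*

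**What the plan says.** The order of blocks is fixed: 8 hours manual, 8 hours automated, 8 hours manual. Protocol 8.2 states "This study is not randomised nor blinded" and gives the reason for the second manual block: "With this setup we can correct for patients that are worsening or improving during the time of the observations". The Summary gives the same purpose. Section 3 describes that block more modestly, as a check that the infant's condition did not change significantly.

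Section 10.1 defines the primary measure as the area outside the SpO₂ target range per hour and says "The significance will be tested with a repeated measurement ANOVA". It names no contrast among the three periods. It adds a conditional rule: if the first and last periods differ significantly, the infant is taken to have changed over time, and "In that case the automated period will be compared with the best of the two observational periods". It does not say whether the best block is chosen for the group or for each infant.

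Section 4.4 plans on a fall in which the "area under the curve was found from 21 to 3", "with a standard deviation of 30", and states "Because of that only 22 patients are needed" in each ventilation stratum.

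**The concern.** Because the order is fixed, treatment and time can be separated only by a comparison that uses both manual blocks. If infants drift steadily, the average of the blocks before and after estimates what manual control would have given in the middle. The rule in 10.1 discards one of those blocks when there is evidence of drift, and keeps the one with the lower area. That is the first block when infants worsen and the last when they improve. In both cases the automated block is set against a period when the infants were in better condition.

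The primary objective is safety and feasibility. A rule that understates benefit and can manufacture apparent harm matters for that objective. The ANOVA raises a different problem: a test of equality across three periods responds to a difference between the two manual blocks even if PRICO does nothing.

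**Working it through.** **Inputs from Protocol 4.4.** Effect e = 21 − 3 = 18; SD 30; 5% significance and 80% power; 22 infants per stratum.

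**The plan's own figure.** n = (SD × (z₀.₉₇₅ + z₀.₈₀)/e)² = (30 × 2.8016/18)² = 21.8, so 22. This reproduces the plan if 30 is the SD of a paired difference and the test is two-sided. Then 22 × 1.1 = 24.2, taken as 24, and 3 × 24 = 72.

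**Assumption.** The documents give no size or shape of drift. I take linear drift d per block over a range, then check step changes. Best is read as the lower area.

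**Algebra.** Let M1 = m, A = m + d − e, M3 = m + 2d.
- If d > 0, the best block is M1, and A − M1 = d − e.
- If d < 0, the best block is M3, and A − M3 = −d − e = |d| − e.
- So A − best = |d| − e in both directions. At |d| = 4.5, 9 and 18, an effect of 18 appears as 13.5, 9 and 0.
- A − (M1 + M3)/2 = (m + d − e) − (m + d) = −e. There is no bias.

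**Step changes of size D.** A step up between blocks 1 and 2, or down between 2 and 3, biases A − best by D against PRICO. In the other two cases the bias is zero.

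**Whole procedure by simulation.** n = 22; normal errors; within-infant SD 30/√2 = 21.2; 100,000 trials per row. M1 and M3 are compared at two-sided 5%. If they differ, A is compared with the manual block that has the lower group mean. If not, A is compared with the mean of both (assumed, since 10.1 names no contrast).

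| Drift per block, absolute | Rule fires | Mean estimated benefit (true 18) | Power | False harm (true effect 0) |
|---|---|---|---|---|
| 0 | 5% | 17.6 | 85% | 3% |
| 3 | 14–15% | 16.9 | 79% | 5% |
| 4.5 | 27% | 15.8 | 72% | 8% |
| 9 | 76–77% | 10.2 | 36% | 25% |
| 18 | 100% | 0 | 2.5% | 76% |

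The fixed contrast gives a mean benefit of 18.0, power of 87% and false harm of about 2.5% in every row.

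**Which rows are plausible.** The area cannot be negative. With improving infants and the planned effect, the automated mean is 21 − |d| − 18, which needs |d| ≤ 3. In the benefit columns, the larger values therefore apply to worsening infants.

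**ANOVA.** With zero PRICO effect, the three-period test is significant in about 5%, 21%, 68% and 99.9% of trials at |d| = 0, 4.5, 9 and 18.

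**Precision.** Var(A − M) = 2 × 450 = 900, SD 30. Var(A − (M1 + M3)/2) = 1.5 × 450 = 675, SD 26.0. The variance falls by 25%, and power at n = 22 (noncentral t) is 77% against 87%.

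**The case against.** **The rule is a prespecified, conservative hurdle.** Section 3 describes the third block as a check. Checking, then using the harder comparator, fits that description. In an unrandomised, unblinded study, a rule that errs against the device guards a claim of benefit. This stands in part. It does not answer the Summary and 8.2, which promise a correction, and it is not conservative for safety, where the error is false harm.

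**The size of the loss is unknown.** This stands. No drift figure is given, and at 3 per block the loss is moderate (79% against 87%). The direction under linear drift does not depend on the size.

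**The alternative is not drift-proof.** This stands. The symmetric contrast is exact only for linear drift. A single step of size D biases it by D/2, toward benefit in two of the four step cases, where the best-block comparison is unbiased. A transient improvement in the middle block biases both methods toward benefit.

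Some stronger readings are tempting but not supported:
- *Choosing the best block per infant is ruinous even without drift.* The lower of two blocks lies on average 21.2/√π = 12.0 below their mean, but 10.1 applies the rule only after a significant difference. With a group-level pre-test and no drift, per-infant choice gives about 84% power and 5% false harm.
- *At 9 per block the plan shows a benefit of only about 7.8, with about 20% power.* Those figures hold only for trials in which the rule fired. Over all trials they are 10.2 and 36%.
- *The ANOVA is biased toward no effect or harm, or leads to false claims of benefit.* Drift makes it significant too often, which is not a bias toward the null. Section 10.1 also goes on to compare blocks: with zero effect and drift of 9, the procedure simulated here declares benefit in under 1% of trials.
- *The 22 per stratum is wrong.* It follows from its own inputs.

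Naming the ANOVA contrast could be left to a statistical analysis plan. The best-block rule could not, because it is explicit protocol text.

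**Conclusion.** The concern holds for the best-block rule. It does not make the correction that the Summary and 8.2 promise. It is biased against PRICO by |d| under linear drift, and by zero or the full step under a single step change. Across drifts of 0 to 9 per block, whole-procedure power falls from about 85% to 36%, against a constant 87% for the fixed contrast, and false harm rises from about 3% to 25%. These sizes rest on the plan's effect of 18, 30 as the paired-difference SD, n = 22, a group-level choice of block, the symmetric contrast when the rule does not fire, and assumed linear drift. They are a range, not an estimate for this trial.

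The ANOVA point is separate and narrower: a significant three-period test should not be reported as evidence on automated against manual control.

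**What to change.** In 10.1, delete the significance pre-test between the manual blocks and the best-block rule. State one primary contrast for every infant: area in the automated block minus the mean of the areas in the two manual blocks, estimated from the repeated-measures or mixed model with a 95% confidence interval. Report manual 1 against manual 3 descriptively, and automated against each manual block as sensitivity analyses. The sensitivity analyses show whether the result depends on linear drift.

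The cost is wording only, with no new data or infants, and the contrast is more precise. The change gives up the harder hurdle for claiming benefit, and the report should say that the contrast is exactly unbiased only for linear drift.
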